³ Forgatch, M. S., Patterson, G. R., Degarmo, D. S., & Beldavs, Z. G. (2009). Testing the Oregon delinquency model with 9-year follow-up of the Oregon Divorce Study. *Development and psychopathology*, *21*(2), 637-660.

⁴ YEF's toolkit of existing research on parenting programmes highlights a lack of evidence about the direct impact of parenting programmes on crime and violence.

trial in the main, efficacy trial rather than recruit, deliver the programme to, and collect outcome data from an additional set of programme participants

To design this project, the Lab has collaborated with two partners. The first is ISII (Implementation Sciences International, Inc.), a research-based, non-profit organisation based in the USA, which implements the GenPMTO programme, in partnership with the programme developers. ISII also trains community practitioners in its use across the world. The second partner is Barnardo's, the UK's largest children's charity, and the delivery partner for the project. Barnardo's bring significant expertise and experience in delivering similar services and working with vulnerable families.

About the rationale for this evaluation

Whilst there is evidence of GenPMTO's impact on a range of outcomes, this is based on studies conducted outside the UK. There is a well-established phenomenon of programmes being transported into new countries and not demonstrating effectiveness when trialled in their new setting, and there are several examples in the UK of failed replication of programmes.^{5,6,7} One often cited explanation for the high volume of null result trials in the UK, in the context of transporting programmes from overseas, is that these programmes haven't undergone the necessary formative work of ensuring they are appropriate, deliverable, and evaluable within the UK context.⁸ These are necessary preparatory steps to a full-scale impact evaluation, and mitigate the risk of expending resources on an extensive trial before the programme has been adapted to the domestic context, which would ultimately yield uninformative results.

By undertaking a staged evaluation approach to GenPMTO, this enables gathering preliminary data on the programmes' feasibility of delivery and evaluability. This facilitates being able to refine the programme and approach to evaluation, to apply learnings from early stages to design a more robust full-scale efficacy trial.

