- 3) Consent and baseline data collection If a family is eligible for the project, the primary caregiver will be approached to consent to participation in the evaluation in the first instance by their referrer and talked through the study information sheet. When a sufficient number of eligible and consenting families are identified, the Lab will get in contact to attempt to collect baseline outcome data. For families that express a preference to receive their intervention in-person, they will be invited to an in-person group survey session where a Lab researcher will introduce the survey and support participants in completing it. For families that express a preference to receive their intervention online, these sessions will be conducted online over video conference software. Families that are not able to attend a scheduled survey session (either in-person, or online) will be permitted to self-complete their survey online at a time of their choosing, but will be able to text or call a Lab researcher for support. At this stage the research team will talk caregivers through the information sheet again, provide an opportunity to ask questions, and ask caregivers to reaffirm their consent to be involved. Those who do not consent to participation in the evaluation or do not provide baseline data will not be included in the project and randomised.
- 4) Randomisation Families (one primary caregiver per family) completing baseline surveys will then be randomised by a researcher at the Lab. Barnardo's will be notified who has been randomised to the GenPMTO group and then reach out to them to schedule their GenPMTO programme. Boroughs will be notified who has been randomised to the control group - these participants will not receive GenPMTO but may be referred to pre-existing 'business as usual' local services.
- 5) Post-test data collection We will attempt to collect outcome data from all families, regardless of whether they were randomly assigned to treatment or control groups, and regardless of how much of the programme they complete (an 'Intention-to-Treat' design). We will reach out to all families approximately 14-weeks after their baseline survey, after the GenPMTO intervention has concluded for participants randomised to the treatment group.

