- For other tranches, randomisation will occur *across* Borough When we successfully recruit 30 participants across *all boroughs* who indicate their preference is to receive the programme *online*, we will use simple randomisation to assign these participants to treatment or control.
- Randomisation, then, is effectively stratified by Borough except for participants who wish to
 receive their service online. We have taken this approach because it will enable us to
 randomise and begin delivery for a subset of participants (those who indicate they are content
 with online delivery) faster and reduce waiting lists, as we will not need to wait for 30 eligible
 referrals within a *single* Borough to initiate these tranches.

Randomisation will take place after families are referred to the study, assessed for eligibility, and after baseline assessment. Caregivers will not be blind to treatment allocation. Randomisation will be implemented using a random number generator (using Stata 16.0).

This will not be a waitlist control study, as this pilot study is designed to test the evaluability of (and if progression to the next stage is achieved, feed into) long-term assessment of programme impact. Boroughs have been advised that control group participants can be supported with other services (i.e. business-as-usual), as they would have done in the absence of this project. This may range from no support, to light-touch support, to formalised parenting programmes like GenPMTO (depending on what services are available within a given Borough, the way the Borough standardly refers families to services, and the needs of the family).

Participants and sample size

Inclusion and exclusion criteria for families

We have carefully considered the inclusion and exclusion criteria for caregivers participating in the pilot study (and have tested these as part of the prior feasibility study). Our aims with these criteria are to:

- 1) Include caregivers who stand to benefit most from participation in the project and, potentially, in GenPMTO.
- 2) Exclude any caregivers for whom the project and/or programme may not be best suited, or may be at an increased risk of harm if they were to participate.

Inclusion criteria

Caregivers are eligible to participate in the study (and to receive GenPMTO, should they be randomised to it) if they:

- Have a CYP between the ages of 8-14.
- Are the primary caregiver (i.e. spend the most time with the CYP and are available to care for them).

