- Providing incentives to the control and treatment groups (£20 per completed survey);
- Ensuring that evaluation activities are designed to be low-impact in terms of burden and time (including offering flexibility in terms of how surveys are completed);

- Where needed, utilising the relationships that Barnardo's and referring practitioners have built with participants to facilitate access and cooperation.
- We will inform participants with sufficient notice about planned survey activities.
- We will monitor rates of attrition, and whether there are differences in rates of attrition based on parent/caregiver ethnicity, gender, age, and in terms of baseline outcomes.

Contamination/spillover

It is possible that within the same geographic area (London borough), some spillover may occur, with caregivers receiving the treatment discussing parenting strategies and what they have learnt in GenPMTO with caregivers in the control group. The likelihood of spillover is deemed to be low however, given that the programme is covering a large geographical area with over 200,000 residents. Moreover, the programme is intensive and involves a variety of roleplay exercises and activities to support parents in developing and implementing new parenting strategies. We believe that any effects are likely to emerge as a result of participation in the full programme, and don't expect that sharing information from the programme would provide the same benefits. Finally, if spillover does occur, we believe this would lead to an improvement in outcomes for the control group, which would likely cause an underestimation of the effect size of the intervention, which is relatively tolerable as a risk (when compared to an overestimation).

Unrepresentative business-as-usual offer

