Inclusivity during recruitment and programme delivery

The Lab will work with Barnardo's as programme delivery partner to ensure that inclusive practices are central to the *recruitment process* and that participant wellbeing is promoted by:

- 1. Being considerate of the sensitivity of the topic area during recruitment
- 2. Providing caregivers with welcoming information documentation, which provides all necessary information about data security, anonymity and the reasons for undertaking research, in plain English
- 3. Offering a flexible and varied range of times for introductory (and other) sessions, and the option of attending sessions remotely via video-link, allowing different groups and individuals the opportunity to participate.

Inclusivity during data collection

The collection of data directly from caregivers will occur via caregiver surveys and caregiver interviews. To ensure that the principle of inclusivity is adhered to during this process, the Lab will work with Barnardo's to:

- 1. Use inclusive and accessible language in all survey and interview questions and guidance;
- Ensure that sufficient numbers of either Lab and/or Barnardo's staff will be present at in-person sessions where caregiver surveys are being administered, to provide assistance or instruction as required;
- Strive for equality of access by enabling online (remote) participation in caregiver surveys and interviews. Access issues could include a lack of time during the day to attend sessions, or distance from an in-person session.
- 4. Training for researchers: Prior to conducting interviews, researchers will complete the NSPCC's Introduction to safeguarding and child protection training.

Wellbeing and safety during surveys and interviews

The Lab is conscious that families who engage in the evaluation could be vulnerable to negative and stressful impacts of the research process. The Lab will work to ensure the wellbeing and psychological safety of individuals during data collection by:

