- 1. Designing interview questions to minimise harm and maximise comfort: The Lab will maximise wellbeing and minimise harm during surveys and interviews by (i) structuring questions to build in complexity and difficulty to increase comfort as rapport to develop, (ii) depersonalising questions to elicit comfort and stronger answers (e.g. instead of 'what do you hate about X', ask 'If you had a magic wand, what 3 things would you change about X?"), (iii) being aware of tension discomfort or distress during the interview, repeating that the interview can be stopped may help participants and repeatedly ask if they want to continue, (iv) ensuring that researchers are aware of places to signpost participants and offer this information, and (v) auditing the questions for their sensitivity within the context before the interview.
- Allowing the participants to choose their environment for participating: Where possible the Lab will allow the interviewees to make decisions about the survey and interview setting(s)
 at their home, a public place or over the phone, enabled by the online conference format.
- 3. **Reminding participants of anonymity and data security**: The Lab will seek to minimise anxiety for caregivers by reminding them that the process is fully anonymous and that all identifiable information will be removed from the transcripts and report.

10. Risks

Risk	Impact	Likelihood	Mitigation
Low participation in research activities by caregivers (including differential attrition and higher drop-out from the control group)	High	Medium	 Providing incentives to the control and treatment groups (£20 per completed survey); Ensuring that evaluation activities are designed to be low-impact in terms of burden and time (including offering flexibility in terms of how surveys are completed); Where needed, utilising the relationships that Barnardo's and referring practitioners have built with participants to facilitate access and cooperation. We will inform participants with sufficient notice
			 about planned survey activities. In particular we will attempt to maintain contact throughout the trial period particularly with control group participants, to remind them of their participation in the study and upcoming opportunities to receive their vouchers. We will monitor rates of attrition, and whether there are differences in rates of attrition based on parent/caregiver ethnicity, gender, age, and

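### Delivery-partner staff may attend and help at post-test survey sessions, so unblinded caregiver reports could be collected under different conditions in the two arms

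*Protocol*

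**What the plan says.** - **Survey sessions.** Section 9 (Inclusivity during data collection) states that "sufficient numbers of either Lab and/or Barnardo's staff will be present at in-person sessions where caregiver surveys are being administered". The purpose given for their attendance is "to provide assistance or instruction as required". The sentence names neither a time point nor an arm.
- **Securing responses.** The attrition part of Risks to study validity (Section 5) and the low-participation row of the Section 10 risk table both list, for use where needed, "utilising the relationships that Barnardo's and referring practitioners have built with participants to facilitate access and cooperation".
- **Barnardo's role.** Section 1 describes the organisation as "Barnardo's, the UK's largest children's charity, and the delivery partner for the project". Under Process, step 4, "Barnardo's will be notified who has been randomised to the GenPMTO group and then reach out to them to schedule their GenPMTO programme"; control families are notified to the Boroughs instead.
- **Blinding.** Randomisation and control group (Section 5): "Caregivers will not be blind to treatment allocation".
- **Outcomes.** In the Outcome measures table, the ECBI (primary) and the SDQ are parent reports on the child, and the PPI and PLOC-SFR are parent self-reports.
- **Who runs the surveys.** Process, step 3, has a Lab researcher introduce and support the baseline session. Step 5 (post-test) gives no setting or staffing. Step 6 encourages caregivers to complete the 6-month survey on their own.

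**The concern.** Unblinded caregiver report already leaves the outcomes open to reporting bias. The usual protection is to collect them at arm's length from the provider and identically in both arms. Here a stated rule allows the provider into the room and lets it help with the form, and nothing withdraws that permission once families have been randomised.

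The direction matters. When discussing spillover, the protocol accepts underestimation as more tolerable than overestimation; a wish to please the provider would act towards overestimation. Risks to study validity covers power, attrition, spillover and the business-as-usual offer, but not reporting bias. Any bias would enter the Table 2 outcomes criterion, where one favourable 95% confidence interval with no unfavourable one rates Green. It would then pass into Stage 4, where the pilot data are to be analysed with the new data. The caregiver survey also collects views on programme delivery, which bear on the acceptability criterion (Green at 80% or more). Those views are especially sensitive to the provider's presence.

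**Working it through.** The protocol states no figure on this point, so there is none to reproduce. The check sets the provisions side by side.

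**1. Does the permission reach post-test?** Methods and data collection schedules caregiver surveys at baseline, post-intervention and 6 months. The Section 9 sentence covers any in-person session at which such surveys are given. Post-test falls within its wording, and "and/or" means that Barnardo's staff alone would satisfy it. No other section takes them out.

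**2. Could their presence mean something different in each arm?**

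| Time point | Barnardo's contact with GenPMTO families | Barnardo's contact with control families | Could conditions differ by arm? |
|---|---|---|---|
| Baseline | Eligibility assessment | Eligibility assessment | No: it precedes randomisation |
| Post-test, about 14 weeks after baseline | Scheduling and up to 14 sessions | None described since eligibility | Yes, if Barnardo's attends |
| 6 months | As above | As above | Little: self-completion is encouraged |

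Sending Barnardo's staff equally to both arms would not remove the difference. The same helper may be the course leader to one caregiver and nearly a stranger to another.

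**3. Can that affect the measurements?** All four instruments are answered by the caregiver, who knows the allocation. The ECBI and SDQ ask for a judgement of the child, and the PPI and PLOC-SFR ask about the caregiver's own parenting, which is what the sessions teach. Courtesy towards the provider would be expected to move treated answers towards improvement. That expectation is reasoning about the design, not a finding in the protocol.

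**4. Does anything block it?** Lab leadership of the session is stated for baseline only. Equal incentives (£20 per completed survey) and collection from all families regardless of attendance concern who responds, not the conditions under which they answer.

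**5. Response effort.** Barnardo's continuing tie is with the treated arm, yet the Section 10 row that relies on it addresses higher drop-out among controls. Two features offset this in part: referring practitioners are named beside Barnardo's, and the same row plans extra contact aimed particularly at controls. Neither requires one common sequence in both arms.

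**6. Size.** The protocol gives no reporting shift, no share of post-tests to be done in person and no share at which Barnardo's would attend. A bias in standard deviations cannot be derived from these inputs.

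**The case against.** The best defence is that the Section 9 sentence is an inclusivity provision meant to ensure enough helpers, and is permissive throughout. The only in-person sessions described in detail are at baseline, where presence cannot depend on arm. Remote participation is enabled and the 6-month survey is mainly self-completed, so exposure may be small. Progression is a balanced judgement, and pilot results are to be read with caution. All of this is correct, and it limits the likely extent. It does not close the gap, because post-test staffing is left open while the one sentence on staffing admits the provider.

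Four stronger readings are not supported:

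- *Outcomes are collected differently by arm.* The protocol neither says nor requires this; it only allows it.
- *Process step 3 and Section 9 contradict each other.* They do not. A Lab researcher can lead a session at which Barnardo's staff also help; Section 9 is simply broader.
- *The bias can be expressed as a share of the expected effect.* Any such figure would divide a guess by a quoted number.
- *The pilot cannot read differential attrition.* Retention is rated separately by arm, attrition differences are monitored, and what works to retain each arm is itself a research question.

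It is also fair to say that barring Barnardo's from all follow-up after randomisation could cost responses, with Green retention set at 90% and planned attrition at no more than 15%. That would be a debatable trade, and the point does not depend on it.

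**Conclusion.** The point holds as a permitted risk, not as an established bias. The protocol allows staff of the delivery partner to be present and to help at in-person post-test surveys, at a time when the only post-randomisation contact it describes for them is with the GenPMTO arm and all outcomes are unblinded caregiver reports. If that permission is used, conditions could differ by arm and favour GenPMTO, in the outcomes and in the acceptability ratings. The documents give no size.

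The conclusion rests on two assumptions: that at least some post-tests take place in person with Barnardo's present, and that caregivers answer somewhat more favourably before their provider. Unblinded report would remain a limitation after the fix, but this added source would be removed. It should be settled in the protocol, because who is in the room is trial conduct and no later analysis can recover it.

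**What to change.** - **Section 9, Inclusivity during data collection.** Limit Barnardo's presence to the pre-randomisation baseline. State that post-test sessions, and any supported 6-month survey, are introduced and supported by Lab researchers only, in the same way in both arms. Record mode and helper for each survey. Repeat this in Process, step 5, where staffing is now open.
- **Attrition text in Section 5 and the matching row in Section 10.** Make one Lab-led reminder sequence the default in both arms. If Barnardo's or a referrer is used to re-establish contact, limit the role to passing on the Lab's invitation, with no part in completing the survey, and record its use by arm. Table 1 allows for self-referrals, so a referrer will not exist for every family; Lab contact has to be the common route.

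The cost is protocol wording and slightly more Lab time at post-test sessions. Lab researchers already run the baseline sessions and give text and telephone support. Barnardo's can still help to reach families, so the retention target is not put at much risk. The version history says that the protocol was published before the first cohort was randomised, so at that date the change could have covered every post-test survey.

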Annex A: Summary of GenPMTO programme using the TIDieR framework

Name: Provide a name or phrase that describes the intervention.	GenPMTO
Why: Describe any rationale, theory, or goal of the elements essential to the intervention.	 Positive parenting practices promote positive child/youth outcomes, and coercive parenting practices disrupt them. As children become adolescents, peers also become mediators of youth outcomes. The core positive parenting practices are: skill encouragement, limit setting, monitoring/supervision, family problem solving, and positive involvement. The programme aims to teach parents effective parenting strategies, increase effective parenting, and reduce deviant peer association, which then mediate programme effects on positive child/youth outcomes. In the short term, the programme aims to reduce children and young people's internalising and externalising behaviour problems. In the longer term, the programme aims to reduce police arrests, increase school functioning, improve social relationships, and reduce substance use. Parents show improved marital relationships, a rise out of poverty, and increased socio-economic status.
What - Materials: Describe any physical or informational materials used in the intervention, including those provided to participants or used in intervention delivery or in training of intervention providers. Provide information on where the materials can be accessed.	 Training materials and implementation guides for practitioners. Materials for parents/caregivers. Materials are purchasable from ISII.
What - Procedures: Describe each of the procedures, activities, and/or processes used in the intervention, including any enabling or support activities.	 Initial training and technical assistance - (ISII) provides extensive training and coaching to local practitioners, some of whom are eventually certified as leaders, mentors, trainers, coaches, or fidelity raters for the following generations of PMTO clinicians. Ongoing fidelity monitoring - Practitioners videotape programme sessions for review and coaching by ISII.

	 Practitioners upload written materials and video recordings to ISII's online platform, and receive feedback. 10- to 14-session parenting programme - Practitioners use active teaching approaches (such as group problem-solving, role-play, and video modelling) to support caregivers in using positive parenting strategies at home.
Who: For each category of intervention provider (such as psychologist, nursing assistant), describe their expertise, background, and any specific training given.	Qualifications required for practitioners depend on the agencies that employ them. Practitioners may have Bachelor's, Master's, or Doctorate level degrees. Practitioners serve in a wide variety of delivery systems including child welfare, youth justice, and child mental health.
How: Describe the modes of delivery (such as face to face or by some other mechanism such as internet or telephone) of the intervention and whether it was provided individually or in a group.	The intervention will be provided in group-format, either face-to-face or online. More broadly, the intervention can be delivered on an individual basis, but this mode of delivery will not be used as part of this project.
Where: Describe the type(s) of location(s) where the intervention occurred, including any necessary infrastructure or relevant features.	The programme can be delivered in out-patient health settings, the home, and community centres/settings. In this project, the programme will be delivered in community centres and settings.
When and how much: Describe the number of times the intervention was delivered and over what period of time including the number of sessions, their schedule, and their duration, intensity, or dose.	The programme can be delivered over different modes (i.e. in-person or online). Sessions are between 90 and 120 minutes each.
Tailoring: If the intervention was planned to be personalised, titrated or adapted, then describe what, why, when and how.	Programme adaptations made as part of the Stage 1 study. These will be reported on in future publications.
Modification: If the intervention was modified during the course of the study, describe the changes (what, why, when, and how).	To be assessed on an ongoing basis as part of the study.

How well (planned): If adherence or fidelity was assessed, describe how and by whom, and if any strategies were used to maintain or improve fidelity, describe them.	Programme developer experts assess practitioner sessions using the FIMP (Fidelity of Implementation Rating System) measure, developed by ISII.
How well (actual): If actual adherence or fidelity was assessed, describe the extent to which the intervention was delivered as planned.	To be assessed on an ongoing basis as part of the study.

